## List of Abbreviations

AE	Adverse event
ALT	Alanine transaminase
ANC	Absolute neutrophil count
AR	Adverse reaction
AST	Aspartate transaminase
BTRIS	Biomedical Translational Research Information System
CBC/diff	Complete blood count with differential
CC	Clinical Center
CFR	Code of Federal Regulations
CRIMSON	Clinical Research Information Management System of the NIAID
CRP	C-reactive protein
CSO	Clinical Safety Office
CTCAE	Common Terminology Criteria for Adverse Events
CYP	Cytochrome P450 isozyme
DCR	Division of Clinical Research
DMARD	Disease-modifying antirheumatic drug
DSMB	Data and safety monitoring board
FDA	Food and Drug Administration
GCP	Good Clinical Practice
GI	Gastrointestinal
GRIS	Genomic Research Integration System
GTT	Green top tube
HRPP	Human Research Protections Program
ICH	International Council on Harmonisation
IL-6	Interleukin 6
IL-6R	Interleukin 6 receptor
IND	Investigational new drug
IRB	Institutional review board
ISM	Indolent systemic mastocytosis
ITT	Intent to treat
IV	Intravenous(ly)
LAD	Laboratory of Allergic Diseases
LTT	Lavender top tube
MC-QoL	Mastocytosis Quality of Life Questionnaire
mITT	Modified intent to treat
mITT2	Second modified intent to treat
mITT3	Third modified intent to treat
MLQ	Mastocytosis Quality of Life Questionnaire
MSAF	Mastocytosis Symptom Assessment Form
MSAS	Memorial Symptom Assessment Scale
NIAID	National Institute of Allergy and Infectious Diseases
NIH	National Institutes of Health
OCRPRO	Office of Clinical Research Policy and Regulatory Operations
OHRP	Office for Human Research Protections

OHSRP	Office of Human Subjects Research Protections
PCR	Polymerase chain reaction
PI	Principal investigator
PP	Per protocol
PT/PTT	Prothrombin/partial thromboplastin time
Q2W	Once every 2 weeks
QoL	Quality of life
SAE	Serious adverse event
SAR	Suspected adverse reaction
SC	Subcutaneous(ly)
SCORMA	Scoring of mastocytosis index
SERF	Safety expedited report form
SRCP	Safety review and communications plan
SST	Serum separator tube
SUSAR	Serious and unexpected suspected adverse reaction
ULN	Upper limit of normal
UP	Unanticipated problem

## Protocol Summary

Full Title:	A Phase 2 Randomized Double-Blinded Placebo-Controlled Study to Evaluate the Safety and Efficacy of Subcutaneous Sarilumab in Improving the Quality of Life in Subjects with Indolent Systemic Mastocytosis
Short Title:	Sarilumab for Treatment of ISM
Clinical Phase:	2
IND Sponsor:	OCRPRO/DCR/NIAID/NIH
Conducted by:	LAD/NIAID
PI:	[name]
Sample Size:	N = 30
Accrual Ceiling:	N = 60
Study Population:	Participants will be aged 18 to 74 years-old who have been diagnosed with indolent systemic mastocytosis (ISM).
Accrual Period:	5 years
Study Design:	This will be a randomized, placebo-controlled double-blinded study. Thirty participants will be randomized (1:1) to receive 8 subcutaneous (SC) injections of 200 mg of sarilumab (trade name Kevzara) or placebo once every 2 weeks (Q2W) for 16 weeks. Participants will be evaluated at each study visit for improvement of symptoms of ISM and safety. Study visits for dose 4, 6, and 8 of study agent administration may be self administered at home without study assessments. After a 12-week washout period, all participants will be offered the opportunity to continue 200-mg sarilumab SC Q2W for 52 more weeks, with regular safety checkups.
Study Duration:	Start Date: October 2018 End Date: July 2027 Participants will be on study for up to 91 weeks, from screening through the end of the 1-year for open-label administration.
Study Agent/ Intervention Description:	Kevzara (sarilumab, Sanofi/Genzyme [Cambridge, MA. USA]), 200 mg/dose or placebo via SC injection Q2W for 16 weeks

(8 doses), with the option to continue sarilumab at 200 mg Q2W for 52 more weeks.

- Primary Objective:** To determine the efficacy and safety of 8 doses of sarilumab in improving the quality of life (QoL) in participants with ISM.
- Secondary Objectives:**
1. To assess the need for symptomatic relief with standard medicines.
  2. To assess the effect of sarilumab on serum tryptase.
  3. To investigate the effect of sarilumab on the allelic frequency of D816V *KIT* in peripheral blood.
  4. To investigate the effects of sarilumab on bone marrow mast cell infiltrates.
- Exploratory Objectives:**
1. To assess the effect of sarilumab on end-organ targets of mastocytosis.
  2. To evaluate the effect of sarilumab on skin manifestations.
  3. To evaluate the effect of sarilumab on markers of bone marrow resorption and deposition.
  4. To determine the long-term safety of sarilumab in participants with ISM.
- Primary Endpoints:**
1. QoL at 16 weeks post-initiation of study drug/placebo using the Mastocytosis Quality of Life Questionnaire (MC-QoL).
  2. Frequency and severity of adverse events (AEs) during the randomized double-blinded placebo-controlled treatment period.
- Secondary Endpoints:**
1. Percent improvement in QoL from baseline to 16 weeks post-initiation of study drug/placebo using the MC-QoL. This is computed as  $[(\text{Baseline QoL} - 16\text{-week QoL})/\text{Baseline QoL}] \times 100$ .
  2. Percent improvement in QoL using scoring of mastocytosis index (SCORMA), Memorial Symptom Assessment Scale (MSAS) the Mastocytosis Quality of Life Questionnaire (MQLQ), and the Mastocytosis Symptoms Assessment Form (MSAF).
  3. Reduction in use of medicines for symptomatic relief.
  4. Reduction in serum levels of tryptase.
  5. Decrease in the allelic frequency of D816V using allele-specific polymerase chain reaction (PCR).
  6. Reduction in percentage infiltrating mast cells in bone marrow.
- Exploratory Endpoints:**
1. Reduction in size of liver and spleen, as visualized by ultrasound.
  2. Reduction in number of cutaneous lesions, as determined by SCORMA and photography.

3. Assessment of metabolic bone disease and bone turnover as determined by the peripheral blood markers, bone-specific alkaline phosphatase, osteocalcin, N terminal propeptide of type I procollagen, and crosslinked telopeptides of type I collagen.
4. Frequency and severity of AEs during the open-label treatment period.

## Précis

Systemic mastocytosis is a disorder caused by clonal mast cell proliferation and release of mast cell mediators including tryptase. As a result, mast cell numbers may increase and affect target organs including the dermis (maculopapular cutaneous mastocytosis/urticaria pigmentosa, flushing), gastrointestinal tract (abdominal pain, diarrhea), skeletal system (osteoporosis), hematological system (anemia, thrombocytopenia), and spleen and liver (organomegaly). Patients with indolent (non-aggressive) systemic mastocytosis (ISM) are not candidates for cytoreductive therapy and are generally treated with symptomatic therapy that only partly decreases symptoms. There is, however, a documented association between severity of mastocytosis and elevated serum levels of interleukin (IL)-6. Furthermore, mast cells have been shown to double their rate of division and exhibit increased reactivity and release of mediators when cultured in the presence of IL-6. In addition, in an animal model of mastocytosis, anti-IL-6 has been shown to slow disease progression. In this study, adults with ISM will thus be randomized and treated with sarilumab, a recombinant monoclonal antibody directed against the IL-6 receptor, or receive placebo. Sarilumab is marketed in the United States as Kevzara (Sanofi/Genzyme [Cambridge, MA, USA ]) and is approved by the Food and Drug Administration for the treatment of rheumatoid arthritis. Binding of sarilumab to the IL-6 receptor inhibits IL-6-associated human mast cell signaling and proliferation with a resultant decrease in proliferation and reactivity (decreased mediator release), and therefore is a rational choice for the treatment of ISM.

In this study, participants will be randomized with approximately half of the participants receiving study drug, which will be administered at 200 mg via subcutaneous (SC) injection once every 2 weeks (Q2W) for a total of 16 weeks. The other participants will receive a placebo administered via SC injection Q2W for 16 weeks. Participants will return for a follow-up visit 2 weeks after the final dose (treatment peak), and then again 12 weeks later. Evaluations at study visits will include quality of life and symptom assessments and measurement of serum tryptase levels. Bone marrow examination will be performed at the onset and conclusion of the study. After the week 28 visit, all participants will have the option to continue sarilumab for 52 more weeks, at 200 mg administered via SC injections. Participants will continue to be monitored on a regular basis for safety concerns, as instructed in the study drug's package insert.

## 1 Background Information and Scientific Rationale

### 1.1 Background on Mastocytosis

Mastocytosis is clonal disorder of mast-cell proliferation that results in an increase in mast cells in the skin, bone marrow, and other organs systems. Clinical features of mastocytosis include flushing, pruritus, abdominal pain, diarrhea, hypotension, syncope, and musculoskeletal pain. These features are attributed to both the local and systemic release of mast-cell mediators. The skin is almost always involved in adult patients with ISM in addition to the clinical features described. Greater than 90% of adult patients with ISM have an activating mutation in *KIT*, the receptor for stem cell factor (mast cell growth factor), which results in ligand-independent activation of KIT that is associated with disease pathogenesis. Life-threatening forms of mastocytosis including aggressive mastocytosis, systemic mastocytosis associated with a hematologic neoplasm, and mast cell leukemia are treated with cytoreductive therapy targeting this receptor, which may prolong life, but does not result in disease remission.

ISM, in contrast, is a less severe systemic variant, and patients with ISM are generally managed over the long term with symptomatic therapy that includes mediator blocking agents like H1 and H2 anti-histamines and leukotriene antagonists. Patients with ISM are not candidates for cytoreductive agents due to potential toxic side effects that outweigh the benefits. Unfortunately, symptomatic therapy is often unsuccessful in controlling symptoms and in most cases, disease continues to progress with both an increase in mast cell burden and symptoms.

## **1.2 Sarilumab**

As developed by Sanofi/Genzyme, sarilumab is a fully human anti-IL-6R $\alpha$  monoclonal antibody that binds membrane-bound and soluble human IL-6R and has been shown to inhibit IL-6 signaling. In 2017, the United States Food and Drug Administration (FDA) approved sarilumab for the treatment of rheumatoid arthritis. The drug's mechanism of action, in addition to its application in related inflammatory disorders (eg, ankylosing spondylitis and uveitis) positions it as a plausible candidate for treatment of patients with systemic mastocytosis.

## **1.3 Scientific Rationale**

Current treatment for ISM is directed at reduction of symptoms and improvement of QoL. The role of IL-6 in mast-cell proliferation and mediator release suggests antagonist therapy has the potential to treat ISM, as well. Antagonist therapy with anti-IL-6R would be expected to decrease the release of mediators from mast cells and possibly mast cell number, thus providing a significant relief of symptoms. This is supported by our experience treating one ISM patient with the IL-6R antagonist tocilizumab, an FDA-approved treatment for rheumatoid arthritis, another disorder associated with IL-6-associated disease. Sarilumab, which is also an anti-IL-6R antibody that is indicated for treatment of rheumatoid arthritis, demonstrates a similar safety profile to tocilizumab. Sarilumab has also demonstrated a greater affinity for human IL-6R compared with tocilizumab, so a clinical study to investigate its use in treating ISM is timely.

## **2 Study Objectives**

### **2.1 Primary Objective**

The primary objective of this study will be to determine the efficacy and safety of 8 doses of sarilumab in improving QoL in participants with ISM.

### **2.2 Secondary Objectives**

The secondary objectives will be:

1. To assess the need for symptomatic relief with standard medicines.
2. To assess the effect of sarilumab on serum tryptase.

3. To investigate the effect of sarilumab on the allelic frequency of D816V *KIT* in peripheral blood.
4. To investigate the effects of sarilumab on bone marrow mast cell infiltrates.

### 2.3 Exploratory Objectives

The exploratory objectives will include:

1. To assess the effect of sarilumab on end-organ targets of mastocytosis.
2. To evaluate the effect of sarilumab on skin manifestations.
3. To evaluate the effect of sarilumab on markers of bone marrow resorption and deposition.
4. To determine the long-term safety of sarilumab in participants with ISM.

## 3 Study Design

[figure not shown]
### 3.1 Description of the Study Design

This is a phase 2, double-blinded, randomized, placebo-controlled study to evaluate the efficacy of sarilumab as treatment for ISM. Patients with ISM will receive either 200 mg of sarilumab or placebo via SC injection Q2W for a total of 16 weeks (8 doses). Participants will return for a follow-up visit 2 weeks after the final dose (treatment peak), and then again 12 weeks later. Participants will be evaluated for clinical improvement of ISM-related symptoms, drug-related AEs, and molecular markers of ISM. After the week 28 visit, all participants will have the option to continue sarilumab for 52 more weeks, at 200 mg administered via SC injections. Participants will continue to be monitored on a regular basis for safety concerns, as instructed in the study drug's package insert.

Throughout the study, if a participant's lab results meet pausing criteria (section 12.6), then at the discretion of the PI, CSO, and data and safety monitoring board (DSMB), the dose may be temporarily reduced to 150 mg until the lab values return to normal.

A schematic of the study design is presented in [Figure 1](#).

#### Figure 1 Study Schedule

## 3.2 Study Endpoints

### 3.2.1 Primary Endpoints

1. QoL at 16 weeks post-initiation of study drug/placebo using the MC-QoL.
2. Frequency and severity of AEs during the randomized double-blinded placebo-controlled treatment period.

### 3.2.2 Secondary Endpoints

1. Percent improvement in QoL from baseline to 16 weeks post-initiation of study drug/placebo using the MC-QoL. This is computed as  $[(\text{Baseline QoL} - 16\text{-week QoL})/\text{Baseline QoL}] \times 100$ .
2. Percent improvement in QoL using SCORMA, MSAS and MQLQ/MSAF.
3. Reduction in use of medicines for symptomatic relief.
4. Reduction in serum levels of tryptase.
5. Decrease in the allelic frequency of D816V using allele-specific PCR.
6. Reduction in percentage infiltrating mast cells in bone marrow.

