#### 5.3 Randomization and Blinding/Unblinding Procedures

Eligible participants will be allocated 1:1 to study agent or placebo. A randomization scheme will be generated by the study statistician who will provide a randomized list of arm assignments to the NIH CC Pharmacy. A permuted block approach, with varying block sizes, will be used for the randomization process.

The participants, the investigators, and all who are involved in the evaluation of the study participants including study monitors and central laboratory personnel are blinded to a participant's treatment assignment until all participants have completed the week 16 visit. The NIH research pharmacist is identified as the unblinded third party who will be in charge of treatment assignment, maintaining study supplies/inventory list, and preparing the blinded study medication for each participant. The NIH research pharmacist will be independent of any study assessments. To maintain blinding, any discussion of the treatment assignment between the clinicians and the pharmacy staff is prohibited until the study is unblinded. Unblinding will occur when the final participant completes their week 28 visit (section 6.2.5), or in the case of early termination or study drug discontinuation, after the participant's final study visit.

Participants will be assigned a screening number after completion of the protocol consent for enrollment in the study in the Clinical Research Information Management System of the NIAID (CRIMSON). The study statistician will generate the randomization codes. These codes will be maintained by the NIH research pharmacist. A study allocation number (1, 2, etc) will be assigned when the participant is ready to be randomized. Randomization is defined as the time that the pharmacy is notified that this new participant, with this study allocation number, is being enrolled. This should coincide with the day that the first dose of study drug is administered. Randomization will continue until there are 30 participants who initiate study drug and have at least the first post-baseline QoL measurement at 4 weeks. Note that participants who do not meet these criteria still remain in the study, and attempts to obtain subsequent QoL measures should be made.

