## 15 Statistical Considerations

### 15.1 Study Hypotheses

The primary hypothesis is that the MC-QoL at 16 weeks will be different in the sarilumab-treated participants than in the placebo participants. This is a two-sided alpha = 0.05 test and will be covariate-adjusted by the baseline MC-QoL score.

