### 15.2 Sample Size Justification

The sample size of 15 per arm is limited by the number of patients available to study. In this section, statistical power is evaluated for a possible treatment effect. The distribution of the total MC-QoL measurement was informed by Siebenhaar et al. Since the data are not normally distributed and the scale is constrained between 0 and 100, a beta distribution with parameters 1.30, 2.41 (multiplied by 100), to match the mean and standard deviation of 35 and 22 as seen in Table 7 of Siebenhaar was used to simulate power. This distribution appears quite consistent with the box plot shown in Figure 1 of Siebenhaar. The Siebenhaar paper also reports a high intraclass correlation of 0.9 for measurements 2 weeks apart, suggesting a strong correlation between the baseline and 16-week scores is plausible; thus, a correlation of 0.7 was assumed in the simulation. While the treatment effect is unknown, power was determined under the assumption that the percentage decline in MC-QoL in the sarilumab-treated arm would be 60% and 10% in the placebo arm (some improvement was anticipated in the placebo arm because these individuals know they might be getting an active treatment). As noted previously, this difference between the arms on MC-QoL is considered clinically meaningful.

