### **15.5 Final Analysis Plan**

Several study populations are defined. The intent-to-treat (ITT) population includes all randomized participants. The modified intent-to-treat (mITT) population includes all participants who received at least one dose of sarilumab or placebo. The second modified intent-to-treat (mITT2) population further excludes the participants with no post-baseline data on the MC-QoL. The third modified intent-to-treat (mITT3) population excludes participants without 16-week MC-QoL data. The per protocol (PP) population only includes all participants with available data on 16-week MC-QoL and who report taking more than 80% of study drug.

The primary analysis will compare the groups with respect to the primary endpoint, the 16-week MC-QoL score in the mITT population using linear regression with an indicator for treatment group and the baseline MC-QoL value as a covariate. While the goal is that all participants will have a 16-week MC-QoL regardless of whether they continue drug throughout, the last observed value of MC-QoL will be carried forward to serve as the primary endpoint in the primary analysis for those participants without 16-week values. (This includes carrying the baseline value

forward, if there are no post-baseline measurements). The test will be two-sided with a 0.05 alpha level.

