While the goal is to assess all participants at 16 weeks, regardless of whether they continue with study drug, it is possible that some participants will have missing MC-QoL at 16 weeks. The planned primary analysis, using last observation carried forward, implicitly assumes that study participants who stop getting QoL assessments will be in a stable state, such that the last observed measurement is a reasonable imputation for the 16 week visit. However, to assess the robustness of these results, several sensitivity analysis will be conducted, that implicitly make different assumptions. We will conduct a mixed effects model analysis incorporating all available MC-QoL measurements (this will test the treatment effect at week 16; specifically it will analyze the post-baseline visit timepoints as categorical, and will adjust for the baseline QoL as a covariate.). Another approach imputes participants with missing data at 16 weeks as having the worst scores with a Wilcoxon rank sum test on percent improvement, will be conducted in the mITT population. If there is more than 15% missing data on the 16-week MC-QoL in the mITT population, inverse probability weighting approaches to the linear regression analysis will be done as well in the mITT and ITT populations. Additionally, if the results remain unclear due to missing data, pattern mixture analyses allowing for worse than expected outcomes in those with missing data may be explored.

Other sensitivity analyses will be conducted regardless of whether there are missing data at 16 weeks. We will repeat the primary analysis in the PP population, the mITT2 and mITT3 populations. We will repeat the regression analysis but with a log transformation to both QoL values. To be robust from non-normality, a Wilcoxon rank sum test will also be used to compare the 16-week QoL values in the various analysis populations. Finally, graphical representation of each participant's MC-QoL trajectories over time, color coded by treatment assignment will be constructed.

Baseline adjusted linear regression and Wilcoxon rank sum test will also be used for the secondary and exploratory endpoints. If critical to interpretation, some sensitivity analyses may be conducted.

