A 95% confidence interval of the difference in median percentage improvement will be calculated using a bootstrap. Similarly, standard normal 95% confidence intervals for difference in mean 16-week values, and difference in the mean change from baseline values will be presented. Graphical presentations of baseline and 16 weeks values changes will be completed.

Exploratory analyses might consider analyses with additional covariates and results within subgroups.

Analyses of AEs will be descriptive by study arm, and will also consider severity of AEs.

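### SCORMA, MSAS, MQLQ and MSAF are defined as percent improvement with no baseline floor; the baseline-adjusted week-16 score should be their named test outcome

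*Combined protocol and SAP*

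**What the plan says.** Section 3.2.2 lists two percent-improvement endpoints. Item 1 is "Percent improvement in QoL from baseline to 16 weeks post-initiation of study drug/placebo using the MC-QoL", with the formula (baseline - week 16)/baseline x 100. Item 2 is "Percent improvement in QoL using SCORMA, MSAS and MQLQ/MSAF", with no formula, time point or rule for low baselines.

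For testing, section 15.5 says "Baseline adjusted linear regression and Wilcoxon rank sum test will also be used for the secondary and exploratory endpoints". It does not say whether the regression outcome is the percent improvement or the week-16 score. It adds: "A 95% confidence interval of the difference in median percentage improvement will be calculated using a bootstrap". It also promises intervals for differences in mean 16-week values and in mean change, but names no instrument for them and does not say that they are baseline-adjusted.

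The primary analysis avoids the ratio. It compares week-16 MC-QoL scores "using linear regression with an indicator for treatment group and the baseline MC-QoL value as a covariate". Section 4.2 requires an MC-QoL score of at least 25% at entry and sets no minimum on SCORMA, MSAS, MQLQ or MSAF.

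**The concern.** Percent improvement divides by each person's own baseline. A participant can qualify on MC-QoL and still start low on another instrument:

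- MSAS (Appendix E) has a box for symptoms the patient did not have.
- MQLQ (Appendix F) scores absent or inapplicable items as 0.
- MSAF (Appendix G) tells participants to enter 0 for symptoms they do not attribute to mastocytosis.
- SCORMA (Appendix D) depends partly on skin extent and lesion intensity.

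In such a participant a small absolute worsening becomes a very large negative percentage. With 15 per arm, a few of these values can swing a mean and weaken the test. These scales are the supporting evidence for the MC-QoL result, so avoidable noise could make them look inconsistent with it. Leaving the outcome scale unnamed also leaves that choice open until after unblinding.

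**Working it through.** **Inputs from the documents.** Sections 15.1 and 15.2: 15 per arm, two-sided 0.05, MC-QoL distributed as 100 x Beta(1.30, 2.41), baseline to week-16 correlation 0.7, baselines under 25 dropped, declines of 60% (sarilumab) and 10% (placebo), scores rounded to integers. Section 5.3: 1:1 allocation.

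**Reproducing the plan's figure.** The Beta has mean 35.0 and SD 22.0, and the worked example in 15.2 returns 0.563 and 0.497, as printed. Simulated power of the week-16 regression is 99.7 to 99.8%, consistent with the stated figure of more than 90%.

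**How far the ratio can fall.** On a 0 to 100 scale the worst value at baseline b is (b - 100)/b x 100.

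- b = 25: (25 - 100)/25 x 100 = -300%.
- b = 5: (5 - 100)/5 x 100 = -1,900%.
- b = 0: undefined.

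With the planning model and a floor of only 1 (assumed), at 60% against 10% the median percent improvement was 40% and the first percentile -350%. As an illustration, an arm of 15 with 14 people at 40% and one at -350% has mean (14 x 40 - 350)/15 = 210/15 = 14%.

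**MC-QoL itself (floor 25).** Power for week-16 regression / regression on percent improvement / Wilcoxon on percent improvement:

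- 60% against 10%: 99.7 / 99.3 / 98.8.
- 50% against 10%: 95.2 / 91.1 / 88.1.
- 40% against 10%: 73.0 / 63.9 / 59.9.

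**A scale without a floor.** Assumed: the same Beta shape, within-scale correlation 0.7, correlation 0.5, 0.7 or 0.9 with MC-QoL, selection on MC-QoL of at least 25, and the scale's own baseline floored at 1 so that the ratio exists. There were 6,000 trials per setting. Entries are power in %, with the loss against week-16 regression in brackets.

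| Decline | Correlation with MC-QoL | Week-16 regression | Regression on % | Wilcoxon on % |
|---|---|---|---|---|
| 60 v 10 | 0.5 | 99.5 | 86 (13.5) | 95 (4.5) |
| 60 v 10 | 0.7 | 99.5 | 94 (5.5) | 96 (3.5) |
| 60 v 10 | 0.9 | 99.7 | 98 (1.7) | 98 (1.7) |
| 50 v 10 | 0.5 | 92 | 65 (27) | 74 (18) |
| 50 v 10 | 0.7 | 94 | 76 (18) | 80 (14) |
| 50 v 10 | 0.9 | 95 | 87 (8) | 86 (9) |
| 40 v 10 | 0.5 | 68 | 41 (27) | 47 (21) |
| 40 v 10 | 0.7 | 70 | 48 (22) | 51 (19) |
| 40 v 10 | 0.9 | 73 | 59 (14) | 57 (16) |

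Reruns moved single cells by up to about 4 points. The weakest, regression on percent at 40 v 10 and correlation 0.5, fell as low as 37% against 67%, a loss of 30. The ranges in the verdict cover these reruns. Zero baselines before flooring were at most 0.04% of participants, so the loss does not come from zeros. Between 28% and 71% of trials had at least one participant below -100%.

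**A different error model.** Assume week 16 = baseline x (1 - decline) x lognormal error with coefficient of variation 0.4. At 40% against 10%, percent improvement then has 75 to 76% power (regression) or 75 to 77% (Wilcoxon), against 66 to 72% for week-16 regression. The ordering reverses.

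**The case against.** The strongest reply is that the plan already covers much of this. Section 15.5 promises a baseline-adjusted regression without fixing its outcome, so the sponsor may intend the week-16 score. It adds a rank test and a bootstrap interval on medians, both resistant to extreme ratios. No alpha, power or decision rule attaches to these endpoints. This stands in part: the gap is one of specification, and the rank test helps. At 60% against 10% and correlation 0.5 it cuts the loss from 13.5 to 4.5 points. It does not close the gap, and at 40% against 10% most of the loss remains. The endpoint definition still names only the ratio.

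Three stronger readings are tempting, and the documents do not support them.

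- A reader might infer that a double-digit power loss is built into the plan. At the protocol's own effect the MC-QoL loss is about 1 point or less. Large losses need a weaker effect or a scale without a floor. The weaker effect is a fair sensitivity case, since section 15.2 calls the effect unknown and its power possibly too optimistic, but it is not the plan's assumption.
- A reader might infer that the MC-QoL ratio is also unbounded below. If the floor of 25 holds at baseline, it cannot pass -300%. The criterion does not say whether the screening or the baseline score counts.
- A reader might infer that percent improvement is always less efficient. Under proportional errors it is not, and the documents do not settle which error model applies.

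**Conclusion.** The point holds for SCORMA, MSAS, MQLQ and MSAF. They are defined as percent improvement, have no baseline floor, and have no other named test outcome. The possibility of undefined or extreme values follows from the definition alone.

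The power cost is conditional. Under the protocol's type of planning model, borrowed for a scale without a floor, it is:

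- about 1 to 14 points (regression) or 2 to 5 points (Wilcoxon) at 60% against 10%;
- about 14 to 30 points (regression) or 16 to 22 points (Wilcoxon) at 40% against 10%.

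Under proportional errors the cost is nil, or a gain of up to about 10 points. The documents give no distribution, correlation or effect for these instruments, so every figure for them is an assumption. The primary analysis and its stated power are unaffected.

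**What to change.** In section 3.2.2 item 2 and section 15.5, state that the main test for each of SCORMA, MSAS, MQLQ and MSAF is a linear regression of the week-16 score on treatment arm, with that instrument's baseline as covariate, as for the primary endpoint. Keep percent improvement for these scales as a descriptive median with the bootstrap interval already planned, and state how a zero baseline is handled there.

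Leave secondary endpoint 1 as a descriptive complement. Redefining it as the week-16 MC-QoL score would only duplicate the primary endpoint.

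The cost is protocol and analysis-plan wording. Appendix A already schedules all four instruments at baseline and week 16, so no new data are needed. The downside is small: the test is then on score points rather than percent, and it is somewhat less powerful if errors turn out to be proportional to baseline.
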